**STUDY DESIGN:**

- Single-arm, open-label, phase II study of vosaroxin in combination with cytarabine in patients with newly diagnosed AML.
- Vosaroxin will be administered intravenously at 90 mg/m^2 on days 1 and 4. Cytarabine will be administered in standard fashion as a continuous infusion of 100 mg/m^2 daily on days 1-7.
  - Patients with evidence of residual leukemia on “Day 14 biopsy” following initial induction will be offered re-induction with intravenous vosaroxin at 70 mg/m^2 on days 1 and 4 in combination with continuous infusion cytarabine at 100 mg/m^2 daily on days 1-7.
- Two-stage design. Forty-one (41) patients will provide 80% power to detect a 20% increase in complete remission rates (from 40% to 60%) with a Type I Error rate of 5%. The design permits one interim look to examine evidence of futility after the first 17 patients are evaluable for response. If  $\leq 7$  patients achieve CR then the likelihood of reaching the goal endpoint of  $\geq 60\%$  remission would be diminished. In this case, the VITAL Study DSMB (consisting of a representative from the funding organization, the study chairs, a biostatistician, and participating investigator to be selected by the study chairs) will review the clinical data to determine the merits of continued enrollment. If  $> 7$  CRs are observed then the second stage will open automatically and increase enrollment to 41 patients.
  - Stage 1: First 17 patients who are evaluable for response prior to futility analysis
  - Stage 2: Patients 18-41 enrolled after futility analysis
- Likelihood-based assessment of the statistical evidence be used to monitor the false discovery rate as data accrue and will provide the option of adding one or two extension cohorts of 10 participants each if the initial trial results are inconclusive.
- Selected Standard of Care Study Procedures:
  - Pre-enrollment marrow aspirate / biopsy to confirm AML diagnosis in accordance with WHO define diagnostic criteria, and to be used for analyses as outlined below in correlative analyses section
  - Echo / MUGA to assess LVEF prior to exposure to induction chemotherapy
  - Repeat marrow aspirate / biopsy at day 14 ( $\pm 2$  days) following initiation of induction therapy to assess disease status

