### 12.2. Sample Size Considerations

In accordance with our desire to maintain a uniform study design, we set a total sample size of 41 participants. An interim futility analysis will be conducted following enrollment of 17 evaluable patients. If  $\leq 7$  patients achieve CR then the likelihood ratio in support of reaching the goal endpoint of  $\geq 60\%$  remission would be diminished and the data would then be reviewed by a DSMB to determine if further enrollment is warranted. If  $> 7$  CRs are experienced by the first 17 evaluable patients, enrollment will automatically proceed to enroll a total of 41 patients. Under this two-stage design, a 60% complete remission rate by the “7+V” combination is at least 3.375 times more likely than a 40% CR rate if 22 or more patients experience CR.

In the context of the planned likelihood assessment the option will be provided to add an extension cohort of up to 20 participants if the initial trial results are inconclusive. The use of a likelihood based extension cohort results in false positive and false discovery rates of 3.7% and 3.9%, respectively.

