### 12.3. Study Design

*Overview:* Two-stage single-arm phase II designs with a single interim look for futility are common in this setting. Simon’s optimal two-stage design is a classic design and remains a popular choice. Herein we propose, in the context of a standard two-stage design, that a likelihood-based assessment of the statistical evidence be used. The unique and informative assessment of the observed evidence provided by likelihood ratios is reason enough to employ the approach.

We will employ the likelihood ratio (LR), not a tail area probability (p-value), to represent the strength of statistical evidence with respect to either a 40% or 60% true CR rate. Likelihood ratios are positive and a LR of 1 indicates completely neutral evidence. Small likelihood ratios ( $LR \ll 1$ ) indicate evidence for the null hypothesis and large likelihood ratios ( $LR \gg 1$ ) indicate evidence for the alternative. The scale of evidence is truly continuous, mapping a gradual shift from weak to moderate to strong evidence.

An important advantage is that, unlike p-values, likelihood ratios have three evidential zones: evidence favoring the null hypothesis, evidence favoring the alternative hypothesis, and weak or inconclusive evidence (i.e., favoring neither hypothesis). Of course, p-values have only two zones: evidence against the null hypothesis ( $p < 0.05$ ) and inconclusive evidence ( $p > 0.05$ ; large p-values do not constitute stronger evidence in favor of the null hypothesis). Moreover, the likelihood false discovery rate is easily quantifiable as  $1/(LR+1)$ . Thus, an observed likelihood ratio of 4 (supporting the alternative) has a false discovery rate of 20%. Lastly, likelihood designs have excellent operating characteristics.

*Parameters and assumptions:* For planning purposes, we assume the complete remission rate of standard induction chemotherapy is 40% in the targeted population of this trial and that the use of Vosaroxin in combination with cytarabine may increase this rate to 60%. We plan to enroll a total of 41 patients, but provide the option of adding an extension cohort of 10 to 20 participants if the initial trial results are inconclusive.

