*Two-stage single-arm phase II designs:* There are many two-stage designs that meet nominal Type I and II Error criteria. We choose a two-stage design with a slightly increased expected sample size (EN) of 25.6 but keeps the two-stage sample size below that of a single-stage study ( $n=42$ ) as follows: In stage I, 17 patients are accrued and the study is stopped only if 7 or fewer patients experience a complete remission (CR). Stopping in this fashion is interpreted as evidence of futility. If 8 or more patients experience a CR, the study continues to accrue an additional 24 participants (for a total of 41). At the end, the study is said to generate evidence in support of the hypothesis that incorporating Vosaroxin into frontline AML induction chemotherapy is worthy of future study if 22 or more patients experience CR (i.e. if the observed response rate is greater than 53%). If frontline induction therapy with Vosaroxin plus standard dose continuous infusion cytarabine fails to improve upon the historical CR rate of 40% with conventional 7+3 induction therapy, the study has a 64% probability of early termination (PET).

A standard (frequentist) two-stage design is unable to handle deviations from its planned design (i.e., when the sample size is anything other than 17 or 41). This occasionally happens in multi-center clinical trials for practical reasons relating to the speed of communication and clinical expediency. Green and Dahlberg introduced flexible designs to that are able to accommodate such deviations from planned designs with minimal impact to their nominal operating characteristics. However, in this case, the Green and Dahlberg criteria result in a 25% PET, which poorly protects patients from ineffective therapy. This is one motivating factor in our choice of employing a likelihood-based assessment of the evidence. The likelihood ratio reveals alternative interim stopping criteria that maintain nominal Type I and Type II Error rates, adding significant logistic flexibility (Table 6). Within the context of standard two-stage design, we believe our proposed design best balances the probability of early termination and expected sample size under the stated constraints.

**Table 6.** Interim stopping rules that are constrained to lie between 30% and 60% of total accrual and have a probability of early termination that exceeds 50%. Type I & II Error rates are below designed nominal levels (5% & 20%).

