With a likelihood design, it can happen that the trial yields weak or inconclusive evidence. Technically this can happen in all standard (i.e., frequentist) two-stage designs as well, but when it does the standard design forces a ‘call’ of either ‘Reject the null’ or ‘Fail to reject the null’ (the assignment depends on how the Type I Error is spent throughout the study and can lead to some uncomfortable circumstances, such as calling evidence supporting the alternative as ‘Fail to reject’ and vice versa). Hence, in likelihood designs, it is desirable to minimize the chance of observing weak evidence. Our proposed two-stage design accomplished this sufficiently, as we next describe, but the important thing to remember is that if the trial does result in weak evidence there is no penalty for accruing additional subjects and reporting the combined evidence (assuming that resources will allow such action). In a likelihood design, the probability of weak evidence is driven to zero by the sample size, so it is always possible to refine inconclusive results, often within limited resource constraints.

Table 7 displays a simulation of the proposed trial, potential outcomes, and their probability of occurrence. Analytic expressions for these probabilities exist, but simulating is simpler and essentially as accurate. Table 2 shows what we expect to happen, on average, for our proposed design and what happens if the sponsor chooses to add patients at the end of the trial to refine weak evidence (if observed). In particular, it shows that the chance of observing weak evidence at the end of the study is ~8%, which can be reduced to ~3% (or ~1%) by adding 10 (or 20) more participants. Importantly, only an additional 54 false positives were observed, which represents a very modest inflation in the Type I Error rate from 4.9% (=247/5000) to 6%, and 286 trials under the alternative achieved sufficient evidence to declare efficacy for an increase in power from 80% (=4026/5000) to 86%. At the end of stage II, the false discovery rate for any type of rejection (i.e., any likelihood ratio greater than or equal to 3.375) is 5.8% (=247/(247+4026)). Clearly, cohort expansion can proceed with minimal rates of unwanted consequences.

**Table 7.** Simulation results for extending the likelihood two stage trial for the purpose of refining weak evidence. Cells contain the number (proportion of 5000) trials in each evidentiary class.

Results Under True Ho:						

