LR Class	Trials at end of two-stage design	Weak evidence	Add 10 patients	Weak evidence	Add 10 patients	Weak evidence
$LR \leq 1/3.375$	1145		207		105	
$1/3.375 < LR < 1$	260	424 (8.5%)	113	179 (3.6%)	35	58 (1.2%)
$1 < LR < 3.375$	164		66		23	
$LR \geq 3.375$	247		38		16	
Results under true Ha:						
$LR \leq 1/3.375$	143		39		16	
$1/3.375 < LR < 1$	148	397 (7.9%)	48	135 (2.7%)	30	134 (1.1%)
$1 < LR < 3.375$	249		87		26	
$LR \geq 3.375$	4026		223		63	

a 64% (3184) and 8.7% (434) trials stopped early for futility under the true null and true alternative hypotheses, respectively.

Under the likelihood evidentiary paradigm observed results are reported as follows (let  $K > 1$  be the pre-specified LR that maintains a certain false discovery rate): 1) sufficiently strong evidence for the null ( $LR \leq 1/K$ ); 2) actionable weak evidence for the null ( $1/K < LR < 1$ ); 3) actionable weak evidence for the alternative ( $1 < LR < K$ ); 4) sufficiently strong evidence for the alternative ( $LR \geq 1/K$ ). We will also report the FDR for the result at hand, i.e.  $1/(LR+1)$ . As detailed below, this trial may recruit additional participants if the observed LR is weak (i.e.,  $1/K < LR < K$ ) with a maximum of 61 participants.

A significant number (~8%) of discoveries under the null and alternate hypotheses for our two-stage design had LR of exactly 3.375. Though such results would allow the conclusion of sufficient activity to warrant further investigation in more definitive trials because it passes nominal Type I and II Error rate criteria, we propose to further evaluate these results in the extension cohorts by setting  $K=4$ , treating those trials with LR's of 3.375 as weak evidence. The PET remains unaffected by this slight change. However, the design that uses  $K=4$  and a total sample size of 61 patients has a false positive rate that decreases to 3.7% and power that increases to 83.7%. This strategy also decreases the false discovery rate to 3.9% (table 8). Hence such a design is quite feasible.

**Table 8.** Simulation results for extending the likelihood two stage trial for the purpose of refining weak evidence for K=4. Cells contain the number (proportion of 5000) trials in each evidentiary class.

Results Under True Ho:						
LR Class	Trials at end of two-stage design	Weak evidence	Add 10 patients	Weak evidence	Add 10 patients	Weak evidence

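### With K = 4, the planned 80% power rests on an extension that is only optional: about 73% with none, 80% with one cohort of 10, 84% with two

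*Combined protocol and SAP*

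**What the plan says.** All references are to the combined protocol and SAP.

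- **Promised rates.** The synopsis (Study Design) and section 3.1 state 80% power at a 5% type I error with 41 patients, for a CR rate of 60% against 40%.
- **Form of the extension.** The synopsis says that the likelihood assessment "will provide the option of adding one or two extension cohorts of 10 participants each if the initial trial results are inconclusive", and section 3.1 agrees. Section 12.2 says that "the option will be provided to add an extension cohort of up to 20 participants if the initial trial results are inconclusive", as does the synopsis (Statistical Plan). Section 12.3 (parameters and assumptions) gives 10 to 20 patients.
- **Who decides.** Section 12.3 introduces its simulations as showing "what happens if the sponsor chooses to add patients at the end of the trial to refine weak evidence". Just before this it makes extension conditional on resources and says "there is no penalty for accruing additional subjects and reporting the combined evidence". After Table 7 it says "this trial may recruit additional participants if the observed LR is weak", with a maximum of 61.
- **Threshold.** Section 12.3 first counts 22 or more CRs of 41 (LR 3.375) as success. After Table 7 it proposes K = 4, which makes 22 of 41 a weak result to be examined further in the extension cohorts.
- **Quoted rates.** For K = 4, section 12.3 gives a false positive rate of 3.7%, power of 83.7% and a false discovery rate of 3.9%, tied to a total of 61 patients. The synopsis and section 12.2 repeat 3.7% and 3.9% for the optional extension without that condition.
- **Sample size.** Section 12.3 gives an expected sample size of 25.6 and says that the design "keeps the two-stage sample size below that of a single-stage study" (n = 42).

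**The concern.** The rates in the text are conditional on a decision that the plan leaves open. Whether to extend, and by how much, is decided in an open-label trial after the CR count at 41 patients is known, and nothing says when a weak result must be extended. A reader of the synopsis or section 12.2 would take the quoted rates as properties of the trial, although they belong to one extension policy.

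Two things are at stake. If K = 4 governs the call at 41 patients and nothing is added, the trial has less power than promised. If the 22-of-41 rule governs and patients are added, the type I error exceeds the stated 5%. The sentence saying that further accrual carries no penalty makes the second risk easy to miss.

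**Working it through.** **Inputs.** From section 12.3: "we assume the complete remission rate of standard induction chemotherapy is 40% in the targeted population", and the combination "may increase this rate to 60" per cent. Stage 1 has 17 patients and stops at 7 or fewer CRs; stage 2 adds 24, for 41. Extensions add 10, then 10 again.

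**Evidence scale.** With rates 0.4 and 0.6, the plan's likelihood ratio reduces to LR = 1.5^(2r − n).

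- 22/41 gives 1.5^3 = 3.375; 23/41 gives 1.5^5 = 7.59.
- At K = 4, strong evidence for the alternative needs 23/41, 28/51 or 33/61. Results of 19 to 22 CRs at 41 are weak.
- At K = 3.375, 22/41 is a success, and only 20 or 21 CRs at 41 are weak.

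**Method.** Exact binomial enumeration: trials with 8 or more CRs in stage 1 are carried to 41, and weak results are then convolved with the binomial count of the added patients.

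**The plan's own figures first.**

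- Early termination under the null: 64.1% (plan: 64%). Expected size: 17 × 0.6405 + 41 × 0.3595 = 25.6 (plan: 25.6).
- 22-of-41 rule: 4.7% / 80.1% (plan: 5% / 80%).
- Power in Table 8 with full extension: (3668 + 342 + 176)/5000 = 4186/5000 = 83.7%, as stated; exact 83.6%.
- False discovery rate: 172/(172 + 4186) = 3.9%, as stated; exact 4.0%.
- False positive rate in Table 8: (125 + 32 + 15)/5000 = 172/5000 = 3.44%; exact 3.45%. The stated 3.7% does not follow from the table. Nor does it fit the other two rates, since 0.037/(0.037 + 0.837) = 4.2%, not 3.9%.

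**Type I error / power by extension path (%).**

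| Extension after a weak result | K = 4, exact | Table 8 counts | K = 3.375, exact | Table 7 counts |
|---|---|---|---|---|
| None | 2.5 / 72.6 | 2.5 / 73.4 | 4.7 / 80.1 | 4.9 / 80.5 |
| One cohort of 10 | 3.1 / 79.8 | 3.1 / 80.2 | 5.5 / 84.4 | 5.7 / 85.0 |
| Two cohorts of 10 | 3.45 / 83.6 | 3.4 / 83.7 | 5.8 / 86.0 | 6.0 / 86.2 |
| Single block of 20 | 3.1 / 82.9 | – | 5.4 / 85.7 | – |
| Two cohorts of 10, only if LR > 1 | 3.3 / 81.7 | – | – | – |

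For example, K = 4 power with two cohorts is 0.7258 + 0.0726 + 0.0376 = 0.8360, and type I error is 0.0251 + 0.0062 + 0.0032 = 0.0345. Without extension, the power gap between the two thresholds, 80.1 − 72.6 = 7.5 points, is the chance of exactly 22/41 under a 60% rate.

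**Sample size at K = 4 with two cohorts.** The expected size is 17 × PET + 41 × (1 − PET) + 10 × P(weak at 41) + 10 × P(weak at 51), where PET is the probability of early termination.

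- Null: 25.63 + 10 × 0.1534 + 10 × 0.0902 = 28.1.
- Alternative: 17 × 0.0919 + 41 × 0.9081 + 10 × 0.1711 + 10 × 0.0935 = 41.4.

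Under this policy, 15% of trials (null) to 17% (alternative) are weak at 41 and so pass the single-stage 42.

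**The case against.** The strongest reply is that K = 4 was introduced for use with the extension cohorts. Section 12.3 itself says that an LR of 3.375 would pass the nominal error criteria, and sections 12.2 and 12.3 keep 22 of 41 as the two-stage criterion. On that reading a trial that never extends is judged at 22/41, and 4.7% / 80.1% matches the promise. This stands as a possible reading. It means that the shortfall depends on which K governs at 41 patients, so the two questions cannot be separated.

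Tables 7 and 8 also print counts at 41, 51 and 61 patients, so the rates for none, one and two cohorts can be derived. That is correct; the fault is that the text quotes the K = 4 error rates and power only for the 61-patient policy.

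On accrual without penalty, the plan can say that the likelihood ratio keeps its meaning whatever the sampling rule, and its next paragraph reports the rise in type I error from 4.9% to 6%. Nothing is hidden, but a plan that also advertises frequentist error rates cannot leave the sentence unqualified.

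Some stronger readings are tempting but not supported:

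- A reader might infer that K = 4 power stays below 80% unless all 20 patients are added. Extensions of 11 to 19 patients give 80.6% to 84.4%, and two of the plan's descriptions allow them. One cohort of 10 falls only 0.16 points short, and Table 8 gives 80.2% with a simulation standard error of about 0.6 points.
- A reader might infer that only the full extension satisfies both 5% and 80%. A single block of 20 at K = 4, extension only when LR > 1 at K = 4, and no extension at K = 3.375 all do.
- A reader might think that the maximum size is undisclosed or that 25.6 is wrong. Section 12.3 states 61, and 25.6 is correct for the two-stage design before extension.

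**Conclusion.** The point holds in this form. If K = 4 governs the call at 41 patients, power is 72.6% without extension, about 7 points under the planned 80%. It is effectively 80% with one cohort of 10 and about 84% with two. If 22 of 41 governs, power is 80.1% without extension, but one or two cohorts take type I error to 5.5% or 5.8% (6.0% from Table 7's counts). At K = 4, type I error stays below 5% on every path in the table.

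The quoted 83.7% and 3.9% belong to the policy in which every weak result is extended up to 61 patients, and the 3.7% should read 3.4% on Table 8's own counts. These results assume the plan's 40% and 60% rates, the 7-of-17 rule applied as a firm stop, and looks at exactly 17, 41, 51 and 61 patients (or 61 alone for a block of 20).

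**What to change.** 1. State in section 12.3 which K governs the call at 41 patients, and so whether 22 of 41 is a success or a weak result.
2. Use one description of the extension in the synopsis (Study Design and Statistical Plan) and in sections 3.1, 12.2 and 12.3.
3. Either pre-specify when a weak result is extended and by how many patients, or keep the option and report type I error and power for each path (none, one cohort, two cohorts). In the second case, give the no-extension figures as the rates that do not depend on the later choice.
4. Correct the 3.7% in the synopsis, 12.2 and 12.3 to agree with Table 8, and say which policy the quoted rates describe.
5. Confine the sentence about accrual without penalty to the likelihood interpretation, or delete it.
6. Beside 25.6, give the expected sample size with extension (K = 4, two cohorts: 28.1 under the null, 41.4 under the alternative).

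The cost is wording and one small table. The sponsor either accepts a less favourable stated power or gives up some discretion. A binding extension would also commit the trial to up to 20 more patients after weak results, including those leaning to the null (527 of the 813 weak null trials in Table 8). That is a trade-off for the sponsor; reporting by path avoids it.

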**STATISTICAL PLAN:**

[figure not shown]
The primary objective of this single-arm, phase II clinical trial is to determine if vosaroxin in combination with standard dose cytarabine as induction chemotherapy can significantly improve the rate of complete remission (CR) in patients with untreated acute myeloid leukemia. Forty-one (41) patients will be enrolled in a two-stage design that permits one interim look to examine evidence of futility. As per convention, the study will not be stopped early on the basis of preliminary evidence of efficacy observed at the end of the first stage (i.e., at the interim look).

Ethical imperatives and resource constraints encourage the exploration of more adaptive designs. Hence we propose, in the context of a standard two-stage design, that a likelihood-based assessment of the statistical evidence be used. An important advantage is that, unlike p-values, which are binary in nature, likelihood ratios have three evidential zones: evidence favoring the null hypothesis, evidence favoring the alternative hypothesis, and weak or inconclusive evidence (i.e., favoring neither hypothesis).

In accordance with our desire to maintain a uniform study design, we set a total sample size of 41 participants. An interim futility analysis will be conducted following enrollment of 17 evaluable patients. If  $\leq 7$  patients achieve CR then the likelihood ratio in support of reaching the goal endpoint of  $\geq 60\%$  remission would be diminished. In this case, the DSMB will review the clinical data to determine the merits of continued enrollment. If  $> 7$  CRs are experienced by the first 17 evaluable patients, enrollment will automatically proceed to enroll a total of 41 patients. Under this two-stage design, a 60% remission endpoint by the “7+V” combination is 3.45 times more likely than a 40% response rate if 22 or more patients experience CR.

In the context of the planned likelihood assessment the option will be provided to add an extension cohort of up to 20 participants if the initial trial results are inconclusive. In this scenario, the use of a likelihood based extension cohort results in false positive and false discovery rates of 3.7% and 3.9%, respectively.

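### A result of 22 CRs in 41 patients is a success under one part of section 12.3 and weak evidence under another, and the headline error rates belong to the second rule without saying so

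*Combined protocol and SAP*

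**What the plan says.** Section 12.3, in its description of the two-stage design, says the regimen "is worthy of future study if 22 or more patients experience CR" among 41. Its text on Table 7 counts any LR of 3.375 or more as a rejection and describes "a very modest inflation in the Type I Error rate from 4.9% (=247/5000) to 6" per cent when weak results are extended.

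Later, section 12.3 notes that a sizeable share of positive trials have an LR of exactly 3.375. It says of them: "Though such results would allow the conclusion of sufficient activity to warrant further investigation in more definitive trials". It nevertheless goes on: "we propose to further evaluate these results in the extension cohorts by setting" K=4, "treating those trials with LR's of 3.375 as weak evidence". It attaches a false positive rate of 3.7%, power of 83.7% and a false discovery rate (FDR) of 3.9% to that design with 61 patients, citing Table 8.

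The synopsis (Statistical Plan) states that a 60% rate "is 3.45 times more likely than a 40% response rate if 22 or more patients experience CR". Section 12.2 makes the same statement with 3.375. Both then give the K=4 rates. In section 12.2 the words are: "The use of a likelihood based extension cohort results in false positive and false discovery rates of 3.7% and 3.9%, respectively". Neither place mentions K. The synopsis (Study Design) and section 3.1 give 80% power and 5% Type I error for 41 patients, and describe the extension as an option.

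**The concern.** This is the decision threshold for the primary endpoint, and it is stated two ways. A trial that ends at 22/41 has shown enough activity under one paragraph and only weak evidence under another. The K=4 rule is worded as a proposal, the extension is optional, and nothing says what happens at 22/41 when no patients are added. In an open-label, single-arm trial, the verdict could then be settled after the result is known.

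The second problem is the headline rates. A reader of the synopsis or section 12.2 sees 22 CRs followed by 3.7% and 3.9%, and will take them to describe the same rule. They apply only if 22/41 is not a success.

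**Working it through.** **Inputs, all from section 12.3.** Null and alternative CR rates 0.40 and 0.60; 17 patients in stage 1, stopping at 7 or fewer CRs; 24 more for a total of 41; success at 22 or more; weak results extended by 10 patients once (51) or twice (61).

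**Step 1: LR.** With these two rates the plan's formula reduces to LR = (0.6/0.4)^r × (0.4/0.6)^(n−r) = 1.5^(2r−n). At n = 41:

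- 19 CRs: 1.5^(−3) = 0.296 = 1/3.375
- 20 CRs: 1.5^(−1) = 0.667
- 21 CRs: 1.5^1 = 1.5
- 22 CRs: 1.5^3 = 3.375
- 23 CRs: 1.5^5 = 7.59

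With K=3.375, the weak results are 20–21 CRs and success starts at 22. With K=4, the weak results are 19–22 and strong evidence starts at 23. The plan does not print 23; it follows from the formula.

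**Step 2: reproduce the base design.** Take X1 ~ Binomial(17, p), stop if X1 ≤ 7, add X2 ~ Binomial(24, p), and declare success if X1 + X2 ≥ 22. At p = 0.4 the probability of early termination is 64.05% and the expected sample size is 17 + 24 × (1 − 0.6405) = 25.6. Both match the plan. Type I error is 4.73% and power 80.1%, which agrees with the stated 5% and 80% and with Table 7 (247/5000 = 4.9%; 4026/5000 = 80.5%).

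**Step 3: both rules, exactly.** Weak outcomes are carried forward with Binomial(10, p) once or twice. A simulation of 2,000,000 trials agrees with the rows that have a binding stop.

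| Rule | Type I error | Power |
|---|---|---|
| K=3.375, 41 patients, no extension | 4.73% | 80.1% |
| K=3.375, weak results extended to 51 | 5.54% | 84.4% |
| K=3.375, weak results extended to 61 | 5.83% | 86.0% |
| K=4, 41 patients, no extension | 2.51% | 72.6% |
| K=4, weak results extended to 51 | 3.13% | 79.8% |
| K=4, weak results extended to 61 | 3.45% | 83.6% |
| 22/41 kept as success, 19–21/41 extended to 61 under K=4 | 5.20% | 85.0% |

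The plan's Table 8 agrees for K=4 at 41 patients: 125/5000 = 2.5% and 3668/5000 = 73.4%.

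**Step 4: how much rests on 22/41.** The probability of ending at exactly 22/41 is 4.73 − 2.51 = 2.2% at a true rate of 40%, and 80.1 − 72.6 = 7.5% at 60%. If that result is extended to 61 under K=4, it ends as follows:

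| End result | True rate 40% | True rate 60% |
|---|---|---|
| Strong for the alternative | 21.6% | 81.0% |
| Still weak | 52.7% | 18.2% |
| Strong for the null | 25.6% | 0.7% |

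**Step 5: the quoted 3.7% and 3.9%.**

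- Table 8 (K=4): false positives 125 + 32 + 15 = 172, and 172/5000 = 3.44%. True positives 3668 + 342 + 176 = 4186, and 4186/5000 = 83.7%. FDR 172/(172 + 4186) = 172/4358 = 3.9%.
- The stated 83.7% and 3.9% follow from Table 8; the stated 3.7% does not. Taken together, 3.7% and 83.7% would give an FDR of 0.037/(0.037 + 0.837) = 4.2%.
- Table 7 (K=3.375, the 22-CR cut-off): 247 + 38 + 16 = 301, and 301/5000 = 6.0%. True positives 4026 + 223 + 63 = 4312. FDR 301/4613 = 6.5%.

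**Step 6: dependence on the interim.** The footnotes to Tables 7 and 8 count trials at or below 7/17 as stopped, as section 12.3 does. The synopsis, section 3.1 and section 12.2 send them to DSMB review instead. If no trial stopped, which is the upper bound, K=3.375 would give 5.32% / 83.9% at 41 patients and 6.79% / 91.7% with extension to 61. K=4 would give 2.70% / 75.0% and 3.90% / 88.9%.

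**The case against.** The best defence is that the plan can be read coherently. The 22-CR rule belongs to the base two-stage design. K=4 governs the evidence classes and the extension, and a 22/41 result still counts if no patients are added, because section 12.3 concedes that it would support further investigation. The change is disclosed and both tables are printed. The 80% and 5% in the synopsis and section 3.1 are correct for the design they describe. The 22-CR sentence in the synopsis and section 12.2 is a statement about the LR, not a success rule. With extension to 61, the choice moves Type I error only from 3.45% to 5.20% and power from 83.6% to 85.0%, and most extended 22/41 results stay positive if the true rate is 60%.

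Much of this stands. The change is not hidden, the error rates stay moderate, and the 3.7% errs on the high side by about one simulation standard error (0.26 points for 5000 trials). But the coherent reading is nowhere written down, and the K=4 text is only a proposal. On that reading, moreover, the 22/41 trials that are not extended count as successes, and the quoted 3.7% and 3.9% assume that none do. One further point is right: under K=4, 7/17 (LR 1/3.375) is itself weak evidence, so a K=4 rule must say that the interim cut-off stays at 1/3.375.

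**Conclusion.** The concern holds and should be corrected before the plan is relied on. The success threshold has two values, 22 and 23 CRs in 41, with exact Type I error and power of 4.7% / 80.1% and 2.5% / 72.6% if no extension is opened. The synopsis and section 12.2 set the rates of the second rule beside the benchmark of the first; the plan's own figures for the first with extension are 6.0% and 6.5%. The 3.7% should read 3.4% by the plan's own table.

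These results assume true rates of 40% and 60% and a binding stop at 7/17; the extended rates also assume that every weak result is extended to the stated size. With a binding stop, Type I error lies between 2.5% and 5.8% under every reading considered, so the fault is an unsettled rule and mismatched rates, not a large loss of error control. The 3.45 in the synopsis (3.375 by the formula) and the fourth reporting class, printed as LR ≥ 1/K where LR ≥ K is meant, are clerical.

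**What to change.** Choose one K, state it in the synopsis, section 12.2 and both parts of section 12.3, and quote only that rule's rates.

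- **Option A, K=3.375.** Success at ≥22/41, ≥27/51 or ≥32/61. State Type I error of about 5.8% and power of 86% if all weak results are extended to 61, and 4.7% / 80.1% without extension.
- **Option B, K=4.** Success at ≥23/41, ≥28/51 or ≥33/61, with 19–22/41 weak. State about 2.5% / 73% at 41 patients, 3.1% / 80% if weak results are extended to 51, and 3.4% / 83.6% only if all are extended to 61. Restate the 5% / 80% in the synopsis and section 3.1 to match, and say that the interim cut-off stays at LR 1/3.375.

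Under either option, say what 22/41 means if no extension is opened. Correct 3.7% to 3.4% wherever the K=4 rate is kept, 3.45 to 3.375 in the synopsis, and the fourth reporting class to LR ≥ K. State that the rates assume a binding interim stop, and reconcile section 12.3 (stop) with the synopsis, section 3.1 and section 12.2 (DSMB review).

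The cost is wording and restated figures. The maximum of 61 patients does not change. Some figures become less favourable: Type I error of about 5.8% under A, or power of about 73% at 41 patients under B.
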